2. OBJECTIVES

Primary Objective

• To assess overall survival (OS).

Secondary Objectives

The secondary objectives of this study are:

- To assess the effect of IL4-R status on overall survival (OS);
- To assess the safety of MDNA55 following CED;
- To determine the objective response rate (ORR) per Response Assessment in Neuro-Oncology (RANO)-based criteria incorporating advanced imaging modalities (conditional on availability of advanced imaging data);
- To assess progression-free survival (PFS).

Exploratory Objectives

The exploratory objectives of this study are:

- To assess the pharmacokinetics (PK) of MDNA55 in peripheral plasma;
- To assess serum anti-MDNA55 antibody titers and, if elevated, determine neutralizing antibody titers;
- To determine the relationship between clinical outcomes and response assessment status by different sets of imaging-based response criteria;
- To perform additional ad hoc efficacy and safety analyses as needed based on the data acquired in this study;
- To assess the performance of the Brainlab catheter during infusion in terms of distribution and convection of the infusate using real time MRI monitoring.

3. STUDY DESIGN

3.1 General Study Design

This is a single-arm, open-label, multicenter study in approximately 52 adults (at least 46 evaluable) with GB that has recurred or progressed (according to standard RANO criteria). The study will be conducted at up to 12 clinical sites following institutional review board approval and completion of informed consent.

Eligible subjects will undergo surgery associated with catheter placement at which time a tissue biopsy will also be performed. MDNA55 will be infused with the objective of achieving coverage of the tumor and the peritumoral margin to the maximum extent possible as indicated by distribution of a co-infused gadolinium tracer observed by MRI. Pre-treatment catheter trajectory planning will be performed with aim to place up to 4 catheters but a minimum of 2, depending upon the tumor size. Planning for catheter placement will only target the enhancing region of the tumor on MRI.

Study duration is 12 months for each subject with the day of catheter placement/ start of infusion being designated as Day 0.

Post-treatment follow-up assessment of safety will be performed 14 days after CED infusion. Thereafter, efficacy and safety assessments will be performed at 30, 60, 90 and 120 days after CED infusion and every 8 weeks thereafter until 360 days of active follow up have been completed. Subjects who discontinue before the Day 360 visit will undergo all the procedures scheduled for the Day 360 visit at the time of discontinuation.

Subjects who complete the Day 360 assessment without disease progression or discontinue early without disease progression will continue to be followed for disease status until progression where possible. After progression (on study or during post-study follow-up), subjects will continue to be followed, where possible, for survival, post-study treatment(s) for GB and imaging for GB until death (or termination of data collection by the Sponsor or withdrawal of consent by the subject).

3.2 Randomization and Blinding

This study is a single-arm design. All subjects will receive active treatment. No randomization will be performed. No blinding procedures are employed.

3.3 Study Treatment

The concentrations of MDNA55 evaluated in this study will be 1.5, 3, 6, and 9 μ g/mL administered in various volumes that do not exceed 240 μ g (the established maximum tolerated dose of MDNA55).

Infusion via each catheter will be initiated at the rate of 3 μ L/min/catheter and gradually increased in a stepwise manner. The infusion flow rate can be adjusted at the discretion of the Investigator during real time MRI (with subject maintained under anesthesia) provided that the flow rate per catheter does not exceed 10 μ L/min. All functioning catheters should be convicting

at similar flow rates. The flow rate should be established such that the duration of infusion is at least 24 hours to a maximum of approximately 48 hours. In the event that only one catheter is functioning, the flow rate may be increased to complete infusion in 48 hours or less but greater than 24 hours. After the real-time MRI infusion monitoring period is completed, the remainder of the infusion will continue with the subject awake. MRI will be performed upon completion of infusion as a final evaluation of MDNA55 infusate distribution.

At the discretion of the Investigator, a subject may be eligible to receive a second administration of MDNA55.

A detailed description of procedures and assessments to be conducted during this study is summarized in the schedule of study assessments in Table 2, taken from the latest protocol version (Version 6.1).

Table 2: Schedule of Events

Evaluation	Screen	Hospitalization				Day 14	Day 30,	Long
		Before Catheter Placement	Catheter Placement	CED Infusion	End of CED Infusion	,	60, 90 120, then q8w	Term F/up
Day	-14 to 0	-24 hrs to 0	0	0-2	1-2 a	14 a	a, b, c	p
Informed Consent d	X							4 9
Hospital Registration		X						
Medical/Oncological History	X	X			X			
Operative & Pathology Reports for Index Tumor (resection/biopsy) ^e		Х						
Confirmation of archived tissue being available for biomarker analysis ^f	X							
MRI	X ^{g1}	$\mathbf{X}^{\mathrm{g}2}$	X	3	XXg4		Xg⁵	
CT	Xg6							
Physical Exam, KPS	X	X			Хq	X	X	38 8
Vital Signs (pulse, respiratory rate, weight and blood pressure)	Х	Х	Xr	Xr	Xs	Х	Х	
Neurological Exam	X	X			X	Х	X	
Standard 12-lead Electrocardiogram (triplicate assessment)	X				Xt			
Serum Pregnancy Test hl	X						X	
Hematology / Serum Chemistry h2	X				Xu	X	X	
Coagulation h3	X				Xu	X	X	
Urinalysis ¹⁴	X							
Pharmacokinetics il	X			2	X	X		2, 3
Immunogenicity ⁱ²	X					X	X	
Pre-anesthesia blood sample i3			X					
Baseline Conditions j	X	X						
Pharmacy Preparation of Infusate 1			X	X				
Catheter placement with biopsy k			Х					
CED Infusion: MDNA55/Gadolinium k				X				
Catheter(s) Removal m					X			

Concomitant Meds/Corticosteroids n	X	X	X	X	X	X	X	
Adverse Events °			X	X	X	X	X	
Telephone Contact p								X

Treatment or visit delays for weekends, public holidays or weather conditions do not constitute a protocol violation

- a Safety assessed after initiation of infusion (during and following CED infusion throughout entire hospitalization period) and safety follow-up to be performed on Days 14 and 30 (± 3 days), and 60, 90, 120, 180, 240, 300 and 360 (± 7 days).
- b Scheduled follow-up to be performed with MRI up to 12 months after CED infusion on Day 30 (± 3 days) and Days 60, 90 and 120, then q8w until Day360 (± 7 days) NOTE: at the Day 300 visit only MRI, physical exam/neurological exam/KPS need be performed.
- Subjects who discontinue before the Day 360 visit will undergo all the procedures scheduled for the Day 360 visit if early termination is between follow-up visit time points with the specific provision that MRI will not be required if last MRI performed was within 2 weeks prior to the early termination date. When early termination is in line with a study follow up visit time point that visit will be considered the early termination time point and no other assessments apart from the respective visit date assessments will be required.
- d ICF can be signed in advanced of the 14 day screening period.
- Operative report to be accessioned.
- f Archived tissue from the resection of the initial GB diagnosis required for biomarker analysis including IL4R IHC, MGMT DNA methylation, and other translational biomarkers.
- g All MRIs acquired throughout entire study schedule will follow will be performed according to imaging protocols outlined in the study specific Image Acquisition Guide.
- g1 Screening MRI to be subject to independent assessment to verify objective radiologic tumor characteristics [e.g. tumor size; subjects must have tumor diameter of ≥ 1 cm x ≥ 1 cm (minimum) to 4 cm in any direction, etc.]; additional image reviews of screening MRI pertaining to evaluation of suitability of subjects for convection may be performed by CED experts; if subject approved for enrollment, screening MRI will also be used for catheter placement planning using iPlan® Flow.
- g2 Pre-operative planning MRI can be performed in one or two MRI exams as required, based on local capabilities; Timing of planning images to support catheter trajectory planning is described in Table 6; Planning MRI images will be registered with iPlan® Flow Infusion planning software to support finalization of catheter trajectory plan.
- g3 On Day 0 MRI performed following catheter placement prior to the start of CED infusion as well as during infusion for real-time MRI infusion monitoring (for approximately 1 hour while subject is maintained under anesthesia) (see Section 6.3 for CED infusion procedure).
- g4 On Day 1 or Day 2 (depending on duration of infusion) MRI performed within 4 hours (ideally within 2 hours) after completion of infusion relative to infusion end date/time; another MRI performed within 18-30 hours after completion of infusion prior to subject being discharged from the hospital.
- g5 MRI performed as part of the scheduled follow-up visits on Days 30, 60, 90, 120 and then q8w thereafter until Day 360 / early termination. For subjects who are progression free, MRIs will continue as per the institution's standard of care schedule until confirmed disease progression.
- g6 CT scan acquisition only required when no CT scan is available within 3 months of planned infusion.
- h1 Females of childbearing potential only at Screening, Days 30 and Day 180
- h2 Hematology: hemoglobin, hematocrit, platelet count, white blood cell (WBC) count, and WBC differential; Serum chemistry: AST, ALT, lactate dehydrogenase (LDH), total bilirubin, indirect bilirubin, alkaline phosphatase, total protein, albumin, sodium, potassium, chloride, carbon dioxide, calcium, phosphorus, blood urea nitrogen (BUN), creatinine, uric acid, and glucose.
- h3 Coagulation: prothrombin time (PT)/PTT/INR (PTT, corrected, if necessary).
- h4 Urinalysis: pH, specific gravity, protein, glucose, ketones, blood, leukocyte esterase, and nitrite. Microscopy required only to follow-up clinically significant abnormal findings.

- il PK assessed at Screening (baseline), as soon as possible but not more than 1 hour following infusion end time, approximately 3 hours following completion of infusion and then (after the ~3 hour sample collection) every 6 hours ± 2 hours until 24 hours or until subject is discharged from the hospital (whichever occurs first) and at Day 14.
- i2 Immunogenicity assessed at Screening (baseline) and at Days 14, 30, 120, 240, and 360/early termination.
- i3 Pre-anesthesia blood draw (within 1 hour of subject be placed under anesthesia), this blood sample collection and processing will use a study specific sample collection kit and require immediate (same day) shipment to central laboratory.
- J Baseline conditions/symptoms will be collected from Screening until Day 0 before subject is anesthetized for catheter placement surgery; any baseline condition or symptom noted prior to catheter placement will be recorded in the Medical History.
- k see Section 6.3; prior to catheter insertion, core tumor biopsy samples (at least 3 cores) will be collected, if the neurosurgeon determines it is possible to harvest viable tumor tissue from along the planned trajectory of the CED catheter(s); biopsy sample tissue collection and processing will use a study specific sample collection kit and require immediate shipment to the central laboratory.
- 1 see Study Pharmacy Manual for infusate preparation and dispensing instructions.
- m Following completion of infusion (only after the end of infusion MRI and at any time prior to subject's discharge from the hospital), the catheters can be removed, and the incisions closed in accordance with institutional practice. Removal of catheters must be performed by a delegated neurosurgeon.
- n All concomitant medications will be collected on the Electronic Data capture (EDC) system from the date of informed consent through 30-day safety period. Thereafter, concomitant medications associated with treatmentrelated SAEs and detailed anti-tumor therapy will be collected. Corticosteroid use will be collected until Day 60 or early withdrawal.
- o All AEs will be collected from catheter placement through the end of study visit and all AEs and SAEs will be followed until resolution, stabilization, data cut-off, or death.
- Subjects who complete the Day 360 assessment without disease progression or discontinue early without disease progression will continue to be followed for disease status until progression. After progression (documented on study or during post-study follow-up), subjects will continue to be followed for survival, post-study treatment(s) for GB and imaging for GB, where possible, until death (or termination of data collection by the Sponsor or withdrawal of consent by the subject).
- q Physical exam and KPS assessments will be performed after completion of infusion when the subject is ambulatory prior to hospital discharge.
- r Vital signs monitoring (without weight parameter) will be performed according to institutional best practice throughout entire surgical workflow for catheter placement and CED infusion; study specific vital signs check points during the surgical workflow are prior to initiation of anesthesia, following placement of all catheters but prior to patient being loaded into MRI machine for the real-time infusion monitoring segment and approximately 1 hour post initiation of infusion; NOTE: Site will record any abnormal vitals observed at any time during surgical vital signs monitoring as unscheduled findings.
- s Vital signs taken after completion of infusion when the subject is ambulatory prior to hospital discharge.
- t ECG (triplicate assessment) will be performed at Screening and immediately following completion of infusion (within 2 hours of infusion end time); triplicate assessment in 3 immediate traces.
- u Blood samples for hematology, serum chemistry, and coagulation (Section 7.2.1) shall be taken in parallel with either the PK blood collection that is performed within 1 hour following completion of infusion or the PK blood collection that is performed ~3 hours following completion of infusion.

4. STUDY ENDPOINTS

4.1 Primary Efficacy Endpoint

• Overall survival, defined as the time from treatment until death.

4.2 Secondary Efficacy Endpoints

- Overall survival by tumor IL4-R status;
 - IL4-R status of tumor will be determined based on archived biopsy from the time of initial diagnosis;
- ORR as determined by an independent central review according to RANO- based criteria
 which may incorporate advanced imaging modalities (e.g. diffusion, perfusion and/or
 TRAMs, conditional upon advanced imaging data being available);
 - ORR is defined as the proportion of subjects who achieved a complete response
 (CR) or partial response (PR) out of all treated subjects;
- PFS, defined as the time from treatment until disease progression or death.

4.3 Other Efficacy Endpoints

- Duration of response (DOR). Defined as the time from first response until disease
 progression (per RANO-based criteria and as determined by an independent central
 review) or death among those subjects achieving a complete response (CR) or partial
 response (PR) to treatment;
- Duration of clinical benefit (DOCB). Defined as the time from first response or disease stabilization until disease progression (per RANO-based criteria and as determined by an independent central review) or death among those subjects achieving tumor control: complete response (CR), partial response (PR), or stable disease (SD);
- To determine the Tumor Control Rate (TCR) defined as the proportion of subjects in whom the best overall response is determined as complete response (CR), partial response (PR) or stable disease (SD) based on different sets of imaging-based response criteria. Use of sub-therapeutic doses of Avastin will also be considered in determination of TCR (and will result in a variant of the TCR being calculated);
- Time to Tumor Progression (TTP). Defined as the time from treatment until tumor progression; does not include death.

4.4 Exploratory Endpoints:

 To determine the relationship between efficacy endpoints (i.e., OS, PFS, DOR, DOCB, TTP) and tumor response category using different sets of imaging-based response criteria;

- To determine the relationship between efficacy endpoints (i.e., OS, PFS, DOR, DOCB, TTP, TCR) and IL4R expression status;
- To determine the relationship between efficacy endpoints (i.e., OS, PFS, DOR, DOCB, TTP) and various prognostic factors (i.e., age, sex, KPS, MGMT status, etc);
- To determine the relationship between efficacy endpoints (i.e., OS, PFS, DOR, DOCB, TTP) and use of concomitant medication (i.e., Avastin, steroids);
- To determine the relationship between efficacy endpoints (i.e., OS, PFS, DOR, DOCB, TTP) and various treatment and drug distribution parameters (i.e., MDNA55 concentration, total dose, volume of infusion, percent tumor coverage, etc.);
- To assess the performance of Brainlab catheter during infusion through real time MRI monitoring;

Note: All exploratory analyses will be conditional upon data being available.

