| STUDY OBJECTIVES: | Primary To assess overall survival (OS) Secondary To assess the effect of IL4-R status on overall survival (OS) To assess the safety of MDNA55 following CED To determine the objective response rate (ORR) per Response Assessment in Neuro-Oncology (RANO)-based criteria incorporating advanced imaging modalities. To assess progression-free survival (PFS) Exploratory To assess the pharmacokinetics (PK) of MDNA55 in peripheral plasma To assess serum anti-MDNA55 antibody titers and, if elevated, determine neutralizing antibody titers To determine the relationship between clinical outcomes and response assessment status by different sets of imaging-based response criteria To perform additional ad hoc efficacy and safety analyses as needed based on the data acquired in this study To assess the performance of the Brainlab catheter during infusion in terms of distribution and convection of the infusate using real time MRI monitoring |
| KEY ENROLLMENT CRITERIA: | In order to be eligible to participate in this study, male and female subjects \geq 18 years of age must have primary (de novo) GB that has recurred or progressed (per standard RANO criteria), a life expectancy > 12 weeks and a Karnofsky performance status (KPS) \geq 70. Subjects must have tumor diameter of \geq 1 cm x \geq 1 cm (minimum) to 4 cm in any direction by pre-interventional magnetic resonance imaging (MRI) within 14 days of planned treatment and not have features which make the tumor a poor target for CED (e.g. significant liquefaction or geometric features not conducive to CED). IL4-R status of tumor will be determined based on archived biopsy from the time of initial diagnosis. |

[figure not shown]
STUDY DESIGN:

This is a single-arm, open-label, multicenter study in approximately 52 adults (at least 46 evaluable) with GB that has recurred or progressed (according to standard RANO criteria). The study will be conducted at up to 12 clinical sites following institutional review board approval and completion of informed consent.

The concentration and volume of MDNA55 will be adjusted based on tumor size such that total dose will not exceed the established maximum tolerated dose (MTD) of 240 µg. Doses up to 180 µg have been used in this study to-date, with no evidence of dose dependency for safety.

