2.3 Exploratory Objectives

Including:

- To assess the pharmacokinetics (PK) of MDNA55 in peripheral plasma
- To assess serum anti-MDNA55 antibody titers and, if elevated determine neutralizing antibody titers
- To perform additional ad hoc efficacy and safety analysis as needed based on the data acquired in this study
- To determine the relationship between clinical outcomes and response assessment status by different sets of imaging-based response criteria
- To assess the performance of the Brainlab catheter during infusion in terms of distribution and convection of the infusate using real time MRI monitoring

[figure not shown]
3 Study Design

This is a single-arm, open-label, multicenter study in approximately 52 (at least 46 evaluable) adults with primary (de novo) GB that has recurred or progressed (according to RANO criteria). The study will be conducted at up to 12 clinical sites following institutional review board approval and completed informed consent.

The concentration and volume of MDNA55 will be adjusted based on tumor size such that total dose will not exceed the established maximum tolerated dose (MTD) of 240 μ g. Doses up to 180 μ g have been used in this study to-date, with no evidence of dose dependency for safety.

Eligible subjects will undergo surgery associated with catheter placement at which time a tissue biopsy will also be performed. MDNA55 infusate will be infused with the objective of achieving coverage of the tumor and peritumoral margin to the maximum extent possible as indicated by distribution of a co-infused gadolinium tracer observed by MRI. Pre-treatment catheter trajectory planning will be performed with aim to place up to 4 catheters but a minimum of 2, depending upon the tumor size. Planning for catheter placement will only target the enhancing region of the tumor on MRI.

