Protocol # MDNA55-05 CONFIDENTIAL Version: v.6.1 MDNA55 is supplied as a sterile frozen solution at a concentration of and labeled according to country-specific regulatory requirements. Storage and Handling Vials will be stored at -70°C (± 10°C); MDNA55 is known to be stable for at least 3 years. Composition of Infusate for CED MDNA55 drug product will be diluted in Elliotts B® Solution to produce an infusate with a final concentration adjusted to ensure the delivery of a total dose of MDNA55 of up to 240 µg based on tumor size, with HSA and Gd-DTPA (commercially available Magnevist®; 469.1 mg/mL; Details on the preparation of MDNA55 infusate are provided in the Pharmacy Manual. Side Effects Complete and updated AE information is available in the current version of the Investigator's Brochure. TREATMENT PLAN MDNA55 will be administered at a fixed concentration. For patients treated under protocol version 5.0, this will be 6.0 µg/mL, unless advised otherwise by the sponsor's medical representative on behalf of the SRC (see section 5.1) and detailed in an updated pharmacy manual. The study is designed to utilize a volume of infusion (Vi) to achieve maximal coverage of the tumor and peritumoral margin. Use of a surrogate tracer (Gd-DTPA) during infusion of MDNA55 will aim to monitor the pattern of coverage of the tumor and peritumoral margin and estimate the volume of distribution (Vd).

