6.1 Dose

The study is designed to utilize a volume of infusion (Vi) individualized for each subject based on tumor size in order to achieve maximal coverage of the tumor and peritumoral margin. Use of a surrogate tracer (Gd-DTPA) during infusion of MDNA55 will aim to monitor the pattern of coverage of the tumor and peritumoral margin and estimate the volume of distribution (Vd). The duration of infusion will be at least 24 hours; however, infusion may continue to approximately 48 hours if required.

In the event of any concerns by the SRC regarding the possibility of related adverse events, reductions to the concentration, volume or rate of administration may be advised via the Sponsor's medical representative and detailed in an updated pharmacy manual. Likewise, the SRC may permit usage of concentrations up to 12 μ g/mL (provided total dose does not exceed 240 μ g (MTD) if ongoing data review suggests a positive benefit-risk.

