7.4.2 Baseline and Disease Characteristics

The following baseline characteristics of the underlying disease will be summarized:

- Karnofsky Performance Score.
- MGMT Status (positive/methylated or negative/unmethylated)
- Steroid use (Yes, No).
- GBM grade
- Diagnostic method of Glioblastoma (CT, MRI, Biopsy).
- Prior Glioblastoma treatment (Surgery, Radiotherapy, Temozolomide, Other Chemotherapy, Investigational, Other).
- Initial diagnosis to 1st relapse (months)
- Initial diagnosis to current relapse (months)
- Initial diagnosis to start of MDNA55 treatment (months)
- Number of prior relapses (1 or 2)
- Max tumor diameter at baseline (cm)
- Tumor volume at baseline (cm3)

- Lymphocyte count
- Height (cm)
- Weight (kg)
- Body mass index (BMI)

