7.7 Efficacy Analyses

7.7.1 Primary Efficacy Analyses

The primary efficacy assessment will be overall survival defined as the date of catheter placement until death from any cause. Subjects who are not known to have died at the time of the analysis will be censored at the date of last contact.

OS= Date of death/Censored – Date of catheter placement +1.

Survival rates at 6, 9, and 12 months and their exact 95% CI for the primary endpoint (OS) along with the estimate for median and its 80%, 90% and 95% CI, will be produced using KM method. KM estimates of OS will also be presented graphically at 6, 9 and 12 months.

Same summaries will be produced for all subgroups and other time-to-event endpoints.

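### Infusion volume follows tumor size, but the SAP relates survival to volume, dose and coverage with no stated adjustment for size

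*SAP*

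**What the plan says.** **How exposure is set.** Protocol 6.1 describes a "volume of infusion (Vi) individualized for each subject based on tumor size in order to achieve maximal coverage". The protocol makes three statements that concentration is also tied to tumor size. The synopsis and Section 3 both say "The concentration and volume of MDNA55 will be adjusted based on tumor size", subject to the 240 µg cap on total dose, and the infusate description in 5.1 says the final concentration is adjusted with reference to tumor size. Section 6 (Treatment Plan) says instead "MDNA55 will be administered at a fixed concentration" and gives 6.0 µg/mL for subjects treated under protocol version 5.0 unless advised otherwise on behalf of the SRC. SAP 3.3 lists four concentrations: 1.5, 3, 6 and 9 µg/mL.

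**What is to be related to outcome.** SAP 4.4 relates OS, PFS, DOR, DOCB and TTP to "various treatment and drug distribution parameters (i.e., MDNA55 concentration, total dose, volume of infusion, percent tumor coverage, etc". All of this is exploratory and conditional on data being available.

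**How.** SAP 7.7.1 gives Kaplan-Meier rates at 6, 9 and 12 months and medians with confidence intervals, and adds "Same summaries will be produced for all subgroups and other time-to-event endpoints". SAP 7.7.1.1 adds forest plots for OS and places the subgroup list in an appendix that was not part of the text available here. SAP 7.7.3 gives no separate method for the dose relations. The available text contains no regression model and no stratification by tumor size.

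**Tumor size in the plan.** SAP 7.4.2 summarizes baseline maximum diameter and tumor volume. SAP 7.4 breaks baseline characteristics down by concentration, by total dose split at the median and by IL4R status, but not by infusion volume or coverage. Protocol 9.2.5.3 lists tumor size as one subset among many and never crosses it with dose or coverage.

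**The concern.** Subjects are not allocated to a volume independently of their disease: the volume is chosen from a baseline feature that may itself predict survival. If larger tumors do worse, a plain high-versus-low volume comparison makes more volume look harmful, or hides a real benefit. Percent coverage has tumor size in its denominator. If smaller tumors are covered more completely, high coverage will look beneficial for the same reason.

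There is no randomized dose comparison in this single-arm trial, so these displays are its efficacy evidence on delivery and dose. A misread curve could steer later development.

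**Working it through.** The plan gives no figure on this point. Its only design figure, power over 80% for the primary test (Protocol 9.1), is not in dispute and nothing below depends on it.

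**Step 1: which exposures are tied to size.**
- Volume: tied directly (Protocol 6.1).
- Coverage: tied through its denominator. The direction is an assumption.
- Total dose = concentration × volume. At a fixed concentration, dose rises with volume and hence with size. If concentration is also adjusted under the cap, it need not. The largest volume the 240 µg cap allows is 240/1.5 = 160 mL, 240/3 = 80 mL, 240/6 = 40 mL and 240/9 = 26.7 mL, so a larger volume at a lower concentration can carry the same dose.
- Concentration: tied to size under three statements in the protocol, and to protocol version under Section 6. Under the second reading, its likely confounder is enrollment period.

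**Step 2: size of the bias, by simulation with no true dose effect.** From the documents: 46 subjects (Protocol 9.1), diameter range 1 to 4 cm (inclusion criterion 5), exponential OS with median about 11.5 months (9.1). Assumed: diameter uniform over that range, the hazard ratio per cm of diameter, and the strength of the dose-size link. Exposure is split at the median, and a Cox model is fitted with and without baseline diameter.

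Setting A uses a chosen dose-size correlation, censoring spread over 12 to 36 months, and large samples to show the bias itself:

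| Correlation | Size HR per cm | Crude high-vs-low HR | Adjusted HR |
|---|---|---|---|
| 0.5 | 1.0 | 1.01 | 1.01 |
| 0.5 | 1.2 | 1.11 | 0.97 |
| 0.5 | 1.35 | 1.22 | 1.00 |
| 0.5 | 1.5 | 1.30 | 1.00 |
| 0.9 | 1.0 | 1.00 | 0.97 |
| 0.9 | 1.2 | 1.27 | 0.99 |
| 0.9 | 1.35 | 1.49 | 1.01 |
| 0.9 | 1.5 | 1.70 | 1.02 |

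At correlation 0 the crude hazard ratio is 0.99 to 1.00 whatever the size effect.

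Setting B makes volume proportional to a sphere of tumor plus an assumed 1 cm margin, with 30% log-scale noise, 46 subjects and 18 months of follow-up. The implied volume-diameter correlation is about 0.89. For size hazard ratios of 1.2, 1.4 and 1.6 per cm, the crude volume hazard ratio is about 1.3, 1.6 and 1.9. With diameter in the model it is about 1.0.

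**Step 3: total dose when concentration varies.** Setting B, with the four SAP concentrations equally mixed, independent of size and without imposing the cap, gives crude total-dose hazard ratios of about 1.15, 1.3 and 1.5. About 30% of the high-dose half then have below-median tumors.

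**Step 4: could the data reveal the bias?** With 46 subjects split 23 versus 23, the hazard ratio detectable with 80% power (two-sided 5%) is exp[(1.96 + 0.84) × 2/√d] for d events. That is about 3.1 at d = 24 and 2.3 at d = 46. The 95% interval runs from the estimate divided by, to the estimate multiplied by, exp(1.96 × 2/√d): 2.23 at 24 events and 1.78 at 46. A confounding bias of 1.3 to 1.9 sits inside that noise and could not be told from a dose effect.

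**The case against.** The strongest case against the point is that SAP 4.4 states no method for the dose relations. Reading them as unadjusted rests on one sentence about subgroups and on the absence of any model. The subgroup appendix and the table shells are outside the available text, so crossed or size-stratified displays cannot be ruled out. The analyses are exploratory, and Protocol 9.2.8 calls the coverage-outcome work descriptive. The baseline tables would show an imbalance by concentration and total dose. Eligibility narrows the size range, and catheter function, flow limits and interruptions would loosen the volume-size link. A size effect of 1.6 per cm means 1.6³ = 4.1-fold hazard across the eligible range, which is an upper illustration.

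Much of this stands and limits the claim. It does not remove it: a baseline table displays an imbalance without correcting it, none is planned by volume or coverage, and nothing in the available text adjusts for size.

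Three stronger readings are tempting and are not supported.
- A reader might infer that high-dose subjects are large-tumor subjects by construction. Steps 1 and 3 show that this holds for total dose only if concentration was fixed across subjects.
- A reader might infer an inflated false-positive rate. In the simulations a Cox test at nominal 5% rejected up to about a third of the time (32% in Setting A, 37% in Setting B), but the available SAP text plans no test of dose, so these are not error rates of this plan.
- A reader might infer that these are the trial's only dose data. SAP 7.8 also summarizes safety by concentration and by volume, with the same weakness.

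**Conclusion.** The point holds for volume and coverage, and for total dose to the extent that it follows volume. It is conditional on tumor size being prognostic within 1 to 4 cm, for which the documents give no effect size. The protocol's reference list includes a study whose title names residual disease volume as a predictor of outcome in recurrent supratentorial glioblastoma. That makes the condition plausible but supplies no number.

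Under the assumed values, the spurious crude hazard ratio is about 1.1 to 1.3 at a dose-size correlation of 0.5 and about 1.3 to 1.9 when volume is tightly tied to size. It is 1.0 if size is not prognostic. For concentration, the confounder may be protocol version or enrollment period instead, and the groups in SAP 3.3 cannot be interpreted until the protocol's statements are reconciled. A reader might infer that the survival result itself is in doubt, but the primary OS analysis makes no comparison by dose. This is a cheap improvement to exploratory analyses.

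**What to change.** In SAP 4.4 and 7.7:
- Next to the crude curves, report OS and PFS (and TTP where events allow) against volume, total dose and coverage from a Cox model that includes baseline maximum diameter or tumor volume. Alternatively, show the curves within tumor-size halves. DOR and DOCB are confined to subsets and may have too few events for two covariates; labeling them is enough.
- For concentration, also account for protocol version. If version and concentration largely coincide, say that their effects cannot be separated.
- Label the crude displays as exploratory and potentially confounded by tumor size, and extend the baseline table in 7.4 to volume and coverage groups.
- Reconcile the protocol synopsis and Sections 3, 5.1 and 6 on whether concentration was fixed or adjusted to tumor size, and state in the SAP how each subject's concentration was actually set.

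The cost is SAP wording and a covariate already collected. Intervals for the dose relations will be wider because dose and size are correlated, which reflects how little independent information on dose there is. Treatment, data collection and the primary analysis do not change.
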